### A. SPECIFIC AIMS

Substantial evidence demonstrates sex and gender differences in the behavioral, biological, and clinical correlates of substance use disorders. Men tend to initiate use earlier and have higher lifetime prevalence rates of disorder, but women demonstrate more severe withdrawal, more rapid progression from first use to disorder, and greater likelihood of comorbid psychiatric disorder. A growing literature suggests that the ovarian hormones progesterone and estradiol may play a key role in these differences. Evidence from preclinical and clinical research suggests that estradiol enhances drug sensitivity and related behavior, while progesterone attenuates drug sensitivity and behavior. As such, recent clinical trials investigating exogenous progesterone as a potential pharmacologic intervention have shown attenuated subjective and physiological effects of cocaine and nicotine in drug-dependent women, and improved cognitive performance in female smokers. While progesterone has shown promise as a treatment for women with cocaine and nicotine use disorder, it has not yet been tested for cannabis.

To date, there are no approved pharmacologic interventions for cannabis use disorder (CUD) despite numerous clinical trials. Cannabis withdrawal is one potential target for CUD medication development research as withdrawal increases risk of relapse. Important gender differences in cannabis withdrawal have been identified warranting gender-based investigation. Several studies have found that women experience more severe and impairing withdrawal symptoms, primarily physiological (e.g. stomach aches, headaches, nausea) and mood-related (e.g. irritability, mood swings), compared to men. As a naturally occurring sex hormone, progesterone may effectively address these gender differences. The proposed pilot study investigates the feasibility and efficacy of exogenous progesterone administration for cannabis withdrawal among female cannabis users.

#### Specific Aim 1: Test the feasibility of exogenous progesterone administration among cannabis users.

*Hypothesis 1:* Exogenous progesterone administration will induce normative elevations in progesterone comparable to the luteal phase of female menstrual cycle and will be well-tolerated by participants.

#### Specific Aim 2: Examine the efficacy of exogenous progesterone on cannabis withdrawal.

*Hypothesis 2:* Compared to placebo, progesterone will attenuate withdrawal symptoms among heavy-cannabisusing women.

# Exploratory Aim: Examine the effect of exogenous progesterone on cognitive functioning during cannabis withdrawal.

*Exploratory hypothesis:* Compared to placebo, progesterone will enhance cognitive functioning among heavy-cannabis-using women.

## **B. BACKGROUND AND SIGNIFICANCE**

#### Overview of the Problem.

Sex and gender differences in behavioral, biological, and clinical correlates of substance use disorders are myriad (Becker et al., 2017), yet there exists a dearth of gender-informed treatment options. Ovarian hormones have been identified as potential mechanisms of these disparities (Moran-Santa Maria et al., 2014), and recent clinical trials have begun to examine their utility as possible pharmacotherapeutic agents (Evans & Foltin, 2006; Fox et al., 2013; Sofuoglu et al., 2001; 2004; 2011). The ovarian hormone progesterone has shown promise as a treatment for female cocaine and nicotine users, but has not yet been tested for cannabis. Gender differences in cannabis withdrawal, which is associated with relapse (Davis et al., 2016), are pronounced and several studies report more severe and impairing withdrawal symptoms in women compared to men (Copersino et al., 2010; Herrmann et al., 2015; [name] et al., 2017). Developing pharmacological interventions for cannabis withdrawal remains an important priority given the significant cognitive, psychiatric, and physical consequences of heavy cannabis use.

Sex and gender differences in substance use disorders are myriad and must be considered in treatment development research. Across substances of abuse men are at greater risk for lifetime use disorder diagnosis (Becker & Hu, 2008). In contrast, females show greater abuse liability, more rapid progression from use to disorder, more severe withdrawal symptoms, and greater barriers to care (Becker et al., 2017). Cannabis withdrawal in particular is one area of disparity worthy of further investigation. Two studies examining "most recent serious quit attempt" have shown that compared to men, treatment-seeking cannabis-dependent women reported more severe withdrawal symptoms, particularly mood (e.g. mood swings, irritability) and physiological symptoms (e.g. nausea, upset stomach) (Copersino et al., 2010; Herrmann et al, 2015). Another study examined acute cannabis withdrawal symptoms (i.e. "past 24 hours") among 302 treatment-seeking adults in a pharmacotherapy trial and found greater impairment in functioning as a result of more severe withdrawal symptoms among women compared to men ([name] et al., 2017). Given the greater severity and impact of cannabis withdrawal in women and the association between cannabis withdrawal and relapse (Davis et al., 2016), targeted gender-based treatment development for cannabis withdrawal is a priority.

Ovarian hormones are an important mechanism of sex and gender differences in substance abuse. A growing literature suggests that the ovarian hormones progesterone and estradiol, which fluctuate naturally during the menstrual cycle, may play a key role in sex and gender differences in substance abuse (Moran-Santa Maria et al., 2014). Preclinical research has shown that when progesterone levels are low (during the estrous phase in rats) females evidence greater cocaine seeking-behavior (Feltenstein & See, 2007) and are more diligent in self-administration of cocaine (Roberts et al., 1989; Hecht et al., 1999) than males. Numerous preclinical studies have also shown progesterone administration to attenuate reinforcing effects of cocaine (Frye, 2007; Evans & Foltin, 2010) and reduce drug-reinstatement and selfadministration of cocaine (Anker et al., 2007; Larson et al., 2007) and nicotine (Mello et al., 2010). One preclinical study examined the effect of pregnenolone, a precursor to progesterone, on THC administration in rats and found suppressed THC-induced effects including hypothermia, locomotor suppression, and analgesia, as well as dampening of neurobiological effects in reward-related brain regions (VTA, NAc) (Vallee et al., 2014). Clinical research in nicotine, amphetamine, and cocaine users supports these findings. Women in the luteal phase of the menstrual cycle, when progesterone is high, showed decreased subjective cocaine (Evans, Haney, & Foltin, 2002; Sofuoglu et al., 1999) and amphetamine (Justice et al., 1999) effects compared to women in the follicular phase, while female smokers randomly assigned to guit during the luteal phase had lower relapse rates than those assigned to guit during the follicular phase (Allen et al., 2008).

**Progesterone may address gender differences in cannabis withdrawal and improve outcomes for female cannabis users.** Recent clinical trials have investigated exogenous progesterone as a potential pharmacologic intervention. Compared to placebo, progesterone has been shown to attenuate subjective and physiological effects of cocaine in female cocaine users (Evans & Foltin, 2006; Sofuoglu et al., 2002; 2004), as well as decrease cue-induced craving and cortisol response in early abstinent cocaine-dependent women (Fox et al., 2013). In a 12-week trial, progesterone reduced weekly cocaine use in post-partum cocaine-dependent women compared to placebo (Yonkers et al., 2014). Exogenous progesterone, compared to placebo, has also been shown to attenuate craving and subjective effects of smoking (Sofuoglu et al. 2001; 2011), and improve cognitive performance in women but not men (Sofuoglu et al., 2011). While progesterone has shown promise as a treatment for women with cocaine and nicotine use disorders, it has not yet been tested with respect to cannabis. Progesterone may effectively target cannabis withdrawal symptoms in women, thus reducing relapse rates improving daily functioning. The proposed pilot study investigates the feasibility and efficacy of exogenous progesterone administration for cannabis withdrawal among female cannabis users.

#### C. PRELIMINARY STUDIES

**Capacity of Research Team.** Completion of the proposed research will require experience with measuring cannabis withdrawal and gender-based substance use disorder research. As detailed below, the research team has the expertise to successfully complete the proposed work and a proven track-record in similar research areas.

**Experience with measuring cannabis withdrawal.** [name] (mentor) has conducted numerous NIH-funded studies with cannabis-dependent individuals that included regular assessment of cannabis withdrawal symptoms (K23DA15540; R21DA018221; R21DA022424; R01DA026782; R21DA034089). In a study of 87 cannabis-dependent individuals ([name] et al., 2011) craving responses to marijuana cues was assessed using the marijuana craving questionnaire (MCQ) and exposure to the cues produced a significant increase in the MCQ total score (p=0.005). Additional clinical trials assessing buspirone for cannabis dependence ([name] et al., 2015), vilazodone for cannabis dependence ([name] et al., 2016), and the effect of oxytocin on craving and stress response in cannabis-dependence all included assessments of cannabis withdrawal. [name] recently completed a pilot study examining a cognitive bias modification paradigm on cue-reactivity in cannabis-dependent adults which also included assessment of withdrawal symptoms (under review). These studies demonstrate the team's ability to assess cannabis withdrawal in cannabis dependent adults.

**Experience with gender-based research.** Drs. [name] and [name] have conducted numerous gender-based studies in substance-abusing populations including as part of the Specialized Center of Research (SCOR) on Sex/Gender Factors Affecting Women's Health (P50 DA016511-14). In recent studies [name] has examined baseline gender differences among treatment seeking cannabis-dependent adults ([name] et al., 2017), which included important findings on withdrawal symptoms, as well as a study on motivation for change and cannabis outcomes in a pharmacotherapy trial ([name] et al., 2016). In addition, recently completed gender-based studies include a gender-based investigation of yohimbine and drug cues on impulsivity in cocaine users (Moran-Santa Maria, Baker, [name], et al., 2016), and a review of menstrual phase cycle research with recommendations for assessment and future research (Allen, [name], et al., 2016).

**Summary.** Our research group has significant experience with measuring cannabis withdrawal and conducting genderbased substance abuse research. Given the experience and resources of the research team, we anticipate timely completion of the current study.

#### D. RESEARCH DESIGN AND METHODS

#### **D1. General Procedures:**

**Study Overview.** The proposed study will investigate the effect of exogenous progesterone on cannabis withdrawal among female cannabis users. Forty heavy-cannabis-using women will be randomized based on nicotine dependent status to receive placebo or progesterone (200mg bid) over a consecutive 5-day period during the early follicular phase of their menstrual cycle and asked to abstain from cannabis. Menstrual phase will be determined by onset of menses and ovarian hormone levels. Following screening, within 3 days of onset of menses, participants will undergo study visit 1 (day 1 abstinence) which includes biochemical, subjective, and cognitive performance assessments, randomization, and medication instructions; they will take their first medication dose that evening. Participants undergo study procedures on study days 2-4 at home and will return to the clinic on study day 5 for repeat assessments. Salivary progesterone and estradiol levels will be collected daily, and cannabis withdrawal will be assessed twice daily, concurrent with medication adherence procedures. Primary outcomes include progesterone levels and cannabis withdrawal symptoms.

**Recruitment.** Women who use cannabis daily or near daily will be recruited from the community based on previously successful techniques used over the past 20 years by the research team. This will include a mix of community, print, and online advertising.

#### Screening and eligibility assessment.

Participants will be screened either by telephone or in person by the trained study personnel. A quick screen will be used to initially determine study eligibility; this questionnaire is focused on inclusion/exclusion psychiatric diagnoses, medical status, current medication regimen, ability and willingness to fill out the necessary assessments and commit to completion of study procedures. Potential subjects will be given a full description of the study procedures and asked to read and sign an IRB-approved Informed Consent Form if they are interested in participating.

## A) Inclusion Criteria

- 1. Able to provide informed consent and function at an intellectual level sufficient to allow accurate completion of all assessment instruments and study procedures.
- 2. Age 18-45, with regular menses (every 25-35 days).
- 3. Report using cannabis at least 5 days per week, for at least the past year.
- 4. Consent to remain abstinent from alcohol for 12 hours prior to study visits, and all other drugs other than cannabis or nicotine for the duration of the study.
- 5. Consent to random assignment.

## **B) Exclusion Criteria**

- 1. Participants who are pregnant, nursing, amennorheic, or using oral contraceptives.
- History of major medical illnesses; including liver diseases, abnormal vaginal bleeding, suspected or known malignancy, thrombophlebitis, deep vein thrombosis, pulmonary embolus, clotting or bleeding disorders, heart disease, diabetes, history of stroke or other medical conditions that the investigator deems as contraindicated for the patient to be in the study;
- 3. Regular use of psychotropic medication (antidepressants, antipsychotics, or anxiolytics) and recent/current psychiatric diagnosis and treatment for Axis I disorders including major depression, bipolar affective disorder, schizophrenia or panic disorder.
- 4. Current suicidal or homicidal risk. Any subject who endorses suicidal ideation will be seen by a licensed clinician in the Addiction Sciences Division who will determine the best course of action to ensure patient safety.
- 5. Known allergy to progesterone or peanuts (vehicle for micronized progesterone).
- 6. Unwilling or unable to maintain abstinence from alcohol 12 hours prior to study visits, and all other drugs other than cannabis or nicotine for the duration of the study.
- 7. Meet DSM-5 criteria for moderate to severe substance use disorder (other than nicotine, cannabis, or alcohol) within the past year.

## **D2. Participant Procedures:**

**Medication administration and adherence monitoring.** *Micronized progesterone (Prometrium; 200mg)*: Progesterone is a hormone released mainly during the luteal phase of the menstrual cycle and pregnancy, and has been used for over 50 years in the treatment of various disorders including ovarian failure, premenstrual symptoms, amenorrhea, dysfunctional uterine bleeding, menopausal symptoms and for contraception (de Lignieres, 1999; Simon, 1995). Because it is poorly absorbed and has extensive first pass metabolism, several synthetic progesterone derivatives have been synthesized and marketed. However, these synthetic progesterone derivatives have additional androgenic, corticosteroid and anabolic effects and have been associated with unfavorable side effects including fluid retention, androgenic effects and alterations in lipid profile (Goodman et al., 1996). Recently, micronized progesterone formulations that can be taken orally have been developed to overcome the poor absorption of progesterone and the unfavorable side effects of the synthetic progesterone (McAuley et al., 1996; Simon, 1995). The safety, tolerability and efficacy of micronized progesterone and subjective measures have been investigated over a wide dose range, from 200 to 2,000 mg/day (Freeman et al., 1995; Gron et al., 1997; Schweizer et al., 1995). Micronized progesterone provides a specific pharmacological tool to investigate the effects of this hormone, devoid of the additional pharmacological effects that synthetic progesterone derivatives have.

Progesterone or placebo dosing will begin at 9pm on study day 1. On study days 2-4 participants will take medication at home at 9am and 9pm, and on day 5 the final dose will be taken at 9am. Capsules will be prepared by the MUSC Investigational Drug Services. Previous studies (Fox et al., 2013; Sofuoglu et al., 2001; 2011) have used twice daily administration during the follicular phase of 200mg progesterone in order to achieve stable levels of progesterone comparable to normal luteal phase levels (2-20 ng/ml). Safety and tolerability of micronized progesterone has been established in numerous studies with nicotine (Sofuoglu et al., 2001; 2011) and cocaine (Evans & Foltin, 2006; Fox et al., 2013; Reed et al., 2011 Sofuoglu et al., 2002; 2004) dependent individuals.

Adherence Monitoring. Participants will record themselves taking their morning and evening medication doses and then submit these videos to research staff via RedCap survey. Subjects may use their personal smartphones for video submission. If they do not have a smartphone, one will be loaned to them during the course of the study, as video submissions may only be completed on a smartphone (cannot be completed on a computer). A survey link will be sent to the subject via text message twice daily. Video capture will occur as part of the RedCap survey. Videos are automatically stored on some Android smartphones, and participants will be informed of that so they can delete the files, if necessary. Participants using iPhones (and using loaner iPhones from our group) will not have stored videos on their phone and nothing will need to be deleted.

**Ovarian Hormones:** *Progesterone* and *Estradiol* will be measured from salivary samples collected using the passive drool method. Saliva samples will be collected daily; in the lab on days 1 and 5, and at home on days 2-4. Participants will be trained on how to collect and store the samples by study personnel on study day 1.

**Cannabis Withdrawal.** The *Cannabis Withdrawal Scale (CWS; Allsop et al., 2011)* will be used to assess cannabis withdrawal symptoms. CWS is a 19-item self-report measure that assesses cannabis withdrawal symptoms in the past 24 hours (sample items: I felt restless; I had a headache; I had trouble getting to sleep at night) on a 10-point Likert scale (0=Not at All to 10=Extremely). To establish a baseline withdrawal score, the CWS will be administered in person on study day 1. CWS will then be administered once on study days 1 and 5, and twice daily on study days 2-4 as part of the RedCap medication adherence survey that will be sent via text message to the participant. Participants will be asked to respond with reference to the past 12 hours.

**Cannabis Abstinence.** Cannabis abstinence will be assessed using self-report, saliva drug testing, and cannabinoid levels. Self-report will be conducted using the TLFB (see *Instrumentation* section). Saliva drug testing will occur in person on Days 1 and 5, and participants will be trained to administer saliva screening. During days 2-4, participants will schedule a Skype/FaceTime call with study personnel and undergo drug screen procedures via teleconference. Cannabinoid levels will be assessed using urine toxicology collected on Days 1 and 5. Creatinine-corrected cannabinoid levels will be compared from Day 1 to Day 5 to confirm abstinence during the study period.

**Cognitive Testing.** The Symbol Digit Modalities Test (SDMT; Smith, 1982), Go/NoGo Inhibitory Control (IC) Task (Chikazoe et al., 2009), and Approach-Avoidance Task (Wiers et al., 2009) will be used to assess cognitive functioning. The SDMT measures sustained attention, response speed, and visuomotor coordination. It involves filling in a blank space below a symbol with the appropriate symbol-paired number as quickly as possible for 90 seconds. The main outcome is number of correct responses. A computerized IC task will be used to assess response inhibition. During the IC task, participants are instructed to press a button in response to common (75% of trials) and rare (12.5%) Go stimuli while inhibiting responding to rare NoGo stimuli (12.5%). The task provides errors of omission and reaction times during Go trials, and errors of commission on NoGo trials, and has been used in substance abusing populations (Froeliger et al., 2017). The AAT will be used to assess cannabis approach bias – a measure of implicit cognitive bias towards cannabis cues. During the AAT, participants are asked to respond to cannabis-related or neutral images by pushing or pulling a joystick based on an irrelevant image feature (i.e. border color). Primary outcome is cannabis approach bias, and a higher score indicates greater bias.

**Nicotine Dependence**: The *Fagerstrom Test for Nicotine Dependence (FTND; Heatherton, et al., 1991)* will be administered at screening to inform randomization procedures.

**Consent and Screening Interview.** Potential participants will present to the Addiction Sciences Division (ASD) Research Clinic and will be given a full description of the study procedures and asked to read and sign an IRB-approved informed consent form. The Mini-International Neuropsychiatric Interview (M.I.N.I.; Sheehan et al., 1998) will assess exclusionary psychiatric and substance use diagnoses during the past year, including frequency of cannabis use. Participants will provide a urine sample, which will first be tested for pregnancy and subsequently for substance use. Past month cannabis and all other substance use will be assessed using the Timeline Follow-Back (TLFB; Sobell & Sobell, 1992). A medical history and physical exam will be conducted to ensure that the individual is eligible to participate. Participants will provide expected date of menses onset for study personnel to follow-up prior to study day 1 visit.

**Tracking period between screening and study day 1 visit:** Following screening visit participants will be asked to track their menstrual cycle and contact the clinic upon menses onset. Study personnel will reach out to participants 3 days prior to expected onset provided at screening as a reminder. Upon menses onset, participants will schedule study day 1 visit to occur within 3 days, or on Monday if onset occurs on the weekend (Friday-Sunday). *Study day 1 must occur on Monday, Thursday, or Friday in order to assure in-person visit on study day 5.* Participants will be asked to begin abstinence on Study Day 1.

**Study day 1 visit:** Participants will present to ASD and undergo urine toxicology, Breathalyzer, saliva testing, and TLFB. After all inclusion criteria and no exclusion criteria have been satisfied, the participant will be randomized to either the experimental (progesterone 200mg bid) or control (placebo) condition based on nicotine dependent status (FTND score of 4 or greater, versus 3 or below). Participants will then provide a saliva sample for progesterone and estradiol quantification, followed by cognitive testing, and then self-report assessments (see *Instrumentation* section). Participants will then receive medication instructions and review medication adherence procedures (see *Adherence* section). Participants will be instructed to take first dose of medication at 9:00pm that evening to minimize sedation. Participants will then be compensated and discharged.

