#### Example study day 1 timeline

Time	Procedure	Duration
9:00 am	Saliva, breathalyzer, utox	15 mins
9:15	TLFB	15 mins
9:30	Saliva sample (hormones)	5 mins
9:35	Cognitive testing	15 mins
9:50	Self-report assessments (FrSBe, CWS, PANAS-X, CUDIT-R)	20 mins
10:10	Medication instructions	20 mins
10:30	Compensate/discharge	
9:00 pm	First medication dose, CWS (at home)	

**Study days 2-4:** Participants will be prompted by RedCap to complete medication adherence and CWS at 9am and 9pm. Each day participants will schedule a Skype/FaceTime call with study personnel to conduct saliva testing and adverse event assessment. Should an adverse event occur, trained personnel will assess via video conference to determine necessary procedures. Participants will also provide a saliva sample for hormone testing. Participants will be provided with labeled tubes for saliva collection and storage. They will fill out the date and time and place in the freezer to be stored until study day 5 when they will bring to ASD clinic for testing.

**Study day 5 visit:** Participants will present to the ASD clinic by 10am for final study visit. They will undergo saliva testing, urine toxicology, Breathalyzer, and TLFB, followed by hormone saliva sampling and cognitive testing. Participants will be debriefed, compensated, and discharged.

Time	Procedure	Duration
9:00am	Last medication dose, CWS (at home)	
9:00	Saliva, breathalyzer, utox	15 mins
9:15	TLFB	15 mins
9:30	Saliva sample (hormones)	5 mins
9:35	Cognitive testing, FrSBe	15 mins
9:50	Compensate/debrief	10 mins
10:00	Discharge	

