## c. Potential Risks

- 1. Risks due to micronized progesterone: Micronized progesterone is generally well tolerated. The most common adverse effect is sedation. Other less common adverse effects include menstrual irregularity, spotting or breakthrough bleeding, dizziness, cramps, nausea, fatigue, headache and breast tenderness (de Lignieres, 1999; Simon, 1995). Other side effects attributed to synthetic progesterone, including depression, fluid retention, pruritus, jaundice, rash and thrombotic disorders, are unlikely to occur. Recently there has been reports of increased risk of stroke, coronary artery disease, venous thromboembolism and breast cancer in postmenapousal women who have been on long-term hormone replacement treatment with estradiol and progestin (medroxyprogesterone) combination (Grady et al., 2002; Hulley et al., 2002; Nelson et al., 2002). While some of these adverse events develop after years of treatment, venous thromboembolism is seen within the first year of treatment (2002b). It is possible that progestins may contribute to thromboembolism seen during estradiol and progestin treatment and thromboembolism is listed in the PDR as one of the adverse events for medroxyprogesterone treatment (PDR, 2002). In contrast to synthetic progestins, progesterone is not known to cause thromboembolism (PDR, 2002).
- 2. Risks due to study procedures: Participants will be asked not to smoke cannabis for 5 days. During this cannabis abstinence period, participants may experience symptoms of cannabis withdrawal such as craving cannabis, mild anxiety, insomnia, irritability, restlessness, stomachache, headache, nausea, loss of energy or appetite, chills, diaphoresis, and feeling depressed.
- 3. Potential risks of rating scales and questionnaires: These are all non-invasive, should add no risk, and have been used without difficulty or any adverse events in our previous studies with this population. The only minor inconvenience could be the time taken to complete them. Some participants may feel uncomfortable disclosing personal thoughts and feelings. Careful efforts aimed at maintaining confidentiality have been effective in previous research, and only participants' code numbers will be recorded on the forms themselves to protect confidentiality.

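### The 12-hour recall window leaves the CWS night-sleep item without a valid answer at 9pm, so morning and evening totals of a primary outcome are not equivalent

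*Combined protocol and SAP*

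**What the plan says.** Section D2, Cannabis Withdrawal, describes the instrument: "CWS is a 19-item self-report measure that assesses cannabis withdrawal symptoms in the past 24 hours". One of the three sample items given is "I had trouble getting to sleep at night". The same paragraph sets a clinic baseline on Day 1 and then the remote schedule: "CWS will then be administered once on study days 1 and 5, and twice daily on study days 2-4". It closes with the recall instruction: "Participants will be asked to respond with reference to the past 12 hours".

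The clock times are in the visit descriptions and example timelines of D2. For Days 2-4: "Participants will be prompted by RedCap to complete medication adherence and CWS at 9am and 9pm". The Day 1 evening entry, at 9pm, pairs the form with "First medication dose, CWS (at home)". The Day 5 entry, at 9am, pairs it with "Last medication dose, CWS (at home)". The Day 1 clinic self-report block, which includes the baseline CWS, starts at about 9:50am.

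Study Overview (D1) names withdrawal symptoms as one of two primary outcomes. Statistical Analyses specifies a repeated-measures mixed model with a random intercept for each woman. It does not define a CWS summary score, a time structure, a morning/evening term or a target contrast.

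**The concern.** The 12-hour window suits 12-hourly forms and avoids overlapping recall, but it does not suit an item about the night. Read literally, the 9pm form asks each woman to rate getting to sleep at night over a period with no night in it. She can answer zero, leave it blank or repeat her morning answer, and different women may choose differently.

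This is a conflict between the stated window and the stated item content, not merely a missing detail. Its consequence is that a 9am total and a 9pm total are different measurements. The baseline is affected too. A form completed at about 9:50am looks back over the previous night under either a 12-hour or a 24-hour window, so no 9pm score is like-for-like with baseline.

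Sleep is also a plausible place for a drug effect. Potential Risks says of progesterone: "The most common adverse effect is sedation". It also lists insomnia among the expected withdrawal symptoms. A reader of the results will want to know whether a lower CWS total reflects more than better sleep, and inconsistent evening answers to a sleep item blur that.

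**Working it through.** **Plan's own figure.** There is none to reproduce. Sample Size gives 40 women (20 per condition) without alpha, power, effect size or SD.

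**Step 1. Windows.** Times are from the D2 timelines, with the 12-hour window applied throughout. The documents do not say whether it also applies to the clinic baseline.

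| Form | Window | Night included | After first dose |
|---|---|---|---|
| Day 1 clinic, about 9:50am | about 9:50pm-9:50am | yes | no |
| Day 1, 9pm | 9am-9pm | no | no |
| Days 2-4, 9am (3 forms) | 9pm-9am | yes | yes |
| Days 2-4, 9pm (3 forms) | 9am-9pm | no | yes |
| Day 5, 9am | 9pm-9am | yes | yes |

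**Step 2. Counts.** After baseline there are 1 + 2×3 + 1 = 8 scores, of which 4 are at 9pm (50%). The Day 1 9pm form is completed with the first dose and covers no time on treatment. After the first dose there are 7 scores, of which 3 are at 9pm (3/7 = 42.9%). The second count is the relevant one for a treatment effect. The first is kept as an upper bound.

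**Step 3. Loss in the raw time-averaged difference.** Let f be the share of scores at 9pm and s the share of the treatment effect on the total carried by night-sleep items. If the evening item carries none of the effect and all totals are averaged, loss = f × s. With one documented item and an even effect, s = 1/19, so the loss is 3/7 × 1/19 = 2.3%, or 1/2 × 1/19 = 2.6%. The last two rows below rest on assumed values of s.

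| s | f = 3/7 | f = 4/8 |
|---|---|---|
| 1/19 (one documented item, even effect) | 2.3% | 2.6% |
| 4/19 (four items assumed, even effect) | 9.0% | 10.5% |
| 1/2 (half the effect assumed to lie in sleep) | 21.4% | 25.0% |

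If women repeat the morning answer at 9pm, the group difference on the item is kept and the loss falls towards zero. The item is then counted twice.

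**Step 4. What that means for power (illustrative).** Assume two-sided alpha 0.05 and a benchmark effect with 80% power at 20 per arm: d = (1.960 + 0.842) × √(2/20) = 0.886. Power after the loss is Φ(0.886 × (1 − loss)/√(2/20) − 1.960), with the SD unchanged. For the three rows this gives 78.2% / 77.9%, 72.2% / 70.8% and 59.5% / 55.6%.

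**Step 5. If the SD shrinks as well.** An item that is always zero in the evening also removes variance. Assume equal item variances, inter-item correlations of 0.1-0.5 and an even effect. For one item at f = 1/2, the effect retained is 0.9737 and the SD retained is 0.9740-0.9757. The standardised effect retained is then 99.8% or more, and power is 79.8-80.0%.

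**The case against.** The strongest case against is that dilution is not shown. Statistical Analyses fixes no contrast, so averaging morning and evening totals is only one possible analysis. A 9am contrast or a daily summary would avoid or change the loss. This stands: dilution is possible, not established.

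A reader might infer that half of the follow-up information on sleep is gone, or that any sleep effect is halved. The documents do not support that. The 9am forms on Days 2-5 cover every night on treatment once, and 3 of 7 post-dose forms are at 9pm, so even if the evening item carried nothing, 4/7 (57%) of its time-averaged effect would remain.

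A reader might also take several of the 19 items to concern night sleep and put a sizeable fraction of the scale at risk. Only three sample items are shown and one concerns the night, so any larger number is an assumption. A share of scale points is also not a share of the treatment effect.

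Finally, both arms answer the same forms and Statistical Analyses calls all results preliminary. Both points are correct, and they rule out reading this as between-arm bias. They do not make the two totals equivalent. A time term with a level for each occasion would absorb the mean difference between morning and evening. It would not restore a group difference on an item that cannot be answered or equalise morning and evening variances, and a linear day term would not absorb even the within-day alternation.

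**Conclusion.** The concern holds as a measurement-validity and precision point on a primary outcome. The stated window leaves the night-sleep item without a valid evening answer and makes 9am and 9pm totals non-equivalent, and likewise the morning baseline and any 9pm score. That follows from the text alone.

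The size does not follow from the text alone. On the one documented item and an evenly spread effect, the loss is at most about 2.3-2.6% of the raw time-averaged difference, and almost nothing on the standardised scale if the SD falls with it. A loss of about 21-25% needs three assumptions together: half the effect lies in sleep, the evening item carries none of it, and all totals are averaged. The sedation statement makes some concentration in sleep plausible, but the documents do not quantify it.

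The change is worth making because it is nearly free and leaves a clearer effect estimate for the larger study that the protocol anticipates.

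**What to change.** - **Form.** Ask the night-sleep item(s) only at 9am, about the night just passed, and omit them from the 9pm form. If the forms are already in use, remove the item(s) from the 9pm score by a scoring rule fixed before unblinding.
- **Baseline.** State the recall window for the Day 1 clinic CWS and make it the same as for the later forms. Treat the Day 1 9pm form as pre-treatment.
- **Model.** Include a morning/evening term and its interaction with group, and name the target contrast. Omitting the item and then averaging totals would leave the Step 3 loss in place. The alternative is a per-day score. On Days 2-4 this is the 9am night-sleep item(s) plus the mean of the two readings on the other items. Day 5 has only a 9am form and needs its own definition, for example the 9am reading alone.
- **Sensitivity analysis.** Report the total without night-sleep items, so that a reader can see whether any difference extends beyond sleep.

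The cost is a REDCap form edit and a few sentences in the analysis section. The total becomes less comparable with the published 24-hour score, but the 12-hour window already gives that up.
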